2.2 Study Design

This is a randomized, double-blind, placebo-controlled study to evaluate the safety, tolerability, efficacy, and PK profile of MEDI0382 titrated from [REDACTED]

administered once daily by subcutaneous (SC) injection for 32 days in subjects with T2DM and renal impairment ($30 \leq \text{eGFR} < 60 \text{ mL/min/1.73 m}^2$). The study has a 14-day run-in period of diet and exercise and continuous glucose monitoring (CGM), a 32-day treatment period and a 28-day follow-up. Forty (40) subjects across multiple study sites will be randomized in two strata (Insulin dose ≥ 20 U/day or Insulin dose < 20 U/day) [REDACTED]. In addition, at least 40% of randomized subjects will have screening eGFR values between 30 and 44 mL/min/1.73 m², inclusive and at least 40% of randomized subjects will have screening eGFR values between 45 and 59 mL/min/1.73 m², inclusive although there is no stratification based on screening eGFR to ensure balance within insulin strata or treatment groups.

Mixed-meal tolerance tests (MMTT) will be performed on Day -5 and Day 32. Subjects will wear a continuous glucose monitoring (CGM) sensor from the start of the run-in period until the first post-treatment follow-up visit. 24-hour ambulatory blood pressure monitoring (ABPM) will be performed 5 times during the study (pre-treatment and 4 during treatment evaluations). Vital signs, ECG, weight, [REDACTED] measurements will be collected during the study.

An interim analysis will be performed using data collected within 12 weeks after the first subject's first dose or after 20 subjects have completed 32 days of dosing, whichever occurs sooner. This interim analysis will be performed to plan Phase 3 studies and will not be used to modify the conduct of this study.

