4.1.4 Subject Enrollment and Randomisation

Study participation begins (ie, a subject is “enrolled”) once written informed consent is obtained. Once informed consent is obtained, a subject identification (SID) number will be assigned by a central system (eg, an interactive voice/web response system, [IXRS]) and the screening evaluations may begin to assess study eligibility (inclusion/exclusion) criteria. The SID number will be used to identify the subject during the screening process and throughout study participation, if applicable.

Approximately 40% of subjects (n = 16) enrolled in the study will have an eGFR of ≥ 30 and < 45 mL/min/1.73 m² and at least 40% (n = 16) will have an eGFR of ≥ 45 and < 60 mL/min/1.73 m². In addition, at least 50% of subjects (n=20) enrolled in the study should be taking insulin at a total daily dose of ≥ 20 units.

A master log of all consented subjects will be maintained at the site and will document all screening failures (ie, subjects who are consented but do not meet study eligibility criteria and/or are not randomised), including the reason(s) for screening failure.

Subjects who fail to meet the inclusion/exclusion criteria (ie, screening failures) should not, under any circumstances, be randomised or receive investigational product. There can be no exceptions to this rule. Subjects who are enrolled, but subsequently found not to meet all the eligibility criteria, should not be randomised or initiated on treatment. If randomisation and treatment initiation occur for a subject found not to meet any eligibility criterion, withdrawal of the subject from the study will be the decision of the medical monitor.

Subjects may be rescreened once if, in the opinion of the investigator, there is a reason to believe they may be eligible.

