2.3 Treatment Assignment and Blinding

An IWRS will be used for randomization to a treatment group and assignment of blinded investigational product kit numbers. Forty (40) subjects will be randomized using a 1:1 ratio to receive either MEDI0382 or placebo with the randomization stratified [REDACTED]

This is a double-blind study in which MEDI0382 and placebo prefilled syringes are identical except the fill volumes are not identical/indistinguishable in appearance. The different fill volumes of MEDI0382 and placebo prefilled syringes and the relative position of the plunger rods will be visually distinct during administration. Although not perfect, the blind will be maintained by having the study drug administered at the clinical site by an unblinded person not involved in the treatment or clinical evaluation of the subjects. This unblinded person will also dispense and receive drug from the subject and reconcile drug accountability. An unblinded site monitor will interact with site unblinded personnel to maintain study blind.

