2.4 Sample Size

Forty subjects (20 completers in the MEDI0382 group and 20 completers in placebo group) will provide > 85% power to detect 18.1% difference between the two treatment groups in percentage change in the MMTT glucose AUC from baseline (Day -5) to the end of 32 days of treatment (Day 32), with a two-sided significance level of 0.1 and assuming the standard deviation of 20%.

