3.4.1.3 Primary Efficacy Analysis

The primary efficacy analysis will be performed using the ITT population. The primary efficacy endpoint, percentage change in MMTT glucose AUC from baseline (Day -5) to the end of treatment evaluation (Day 32) will be analyzed using an analysis of covariance (ANCOVA) model. The model will include fixed effect for treatment (MEDI0382 or Placebo) with the baseline AUC used as a covariate. The treatment groups will be considered statistically significant if the two-sided significance level is less than 0.10.

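### Screening eGFR has recruitment quotas but is neither stratified on nor included in the primary ANCOVA, so a chance imbalance between arms would go unadjusted; adding it is a cheap improvement.

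*SAP*

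**What the plan says.** SAP 2.2 and Protocol 3.2.2, 4.1.2 and 4.1.4 set targets for two screening eGFR bands, 30 to below 45 and 45 to below 60 mL/min/1.73 m². For the upper band, Protocol 4.1.4 states that "at least 40% (n = 16) will have an eGFR of ≥ 45 and < 60 mL/min/1.73 m²". For the lower band the SAP asks for at least 40%, while the current protocol asks for approximately 40% (16 subjects).

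These targets fix totals across the trial, not the split between arms. The SAP says so itself: "there is no stratification based on screening eGFR to ensure balance within insulin strata or treatment groups". The visible stratification factor is insulin dose, at or above versus below 20 U/day.

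On the primary model, SAP 3.4.1.3 states: "The model will include fixed effect for treatment (MEDI0382 or Placebo) with the baseline AUC used as a covariate". Protocol 4.8.3.1 gives the same two terms. The primary subgroup analyses in SAP 3.4.1.4 use insulin stratum and baseline HbA1c, not eGFR. SAP 3.3.2 lists screening eGFR and its two bands among the baseline characteristics that may be summarised.

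**The concern.** Renal function defines this population, and the sponsor thought its spread important enough for quotas. With 20 subjects per arm, randomisation alone can leave the arms visibly different on it. If eGFR also predicts the glucose response, part of the observed treatment difference would then reflect renal function, and an adjustment chosen after unblinding would be open to challenge. Screening eGFR is an entry criterion, so every eligible randomised subject has a value, and adjusting for it needs no new data.

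**Working it through.** **The plan's own power figure.** SAP 2.4 bases the size on "Forty subjects (20 completers in the MEDI0382 group and 20 completers in placebo group" (10% two-sided level, SD 20) and says that this "will provide > 85% power to detect 18.1% difference between the two treatment groups".

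- Standard error = 20 × √(2/20) = 6.32.
- Noncentrality = 18.1 / 6.32 = 2.86.
- Power = 88.8% by the normal approximation and 87.8% by the noncentral t distribution (37 or 38 df). Both exceed 85%, so the figure reproduces. I use 87.8% as the reference.

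**Chance of imbalance.** Let K of the 40 subjects be in the lower band, with two arms of 20. The lower-band count in one arm is hypergeometric(40, K, 20). This ignores the insulin stratification and any redacted features of the randomisation. For K = 16:

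| Difference between arms | Probability |
|---|---|
| 2 or more subjects (10 percentage points) | 0.75 |
| 4 or more, e.g. 10 v 6 (20 points) | 0.333 |
| 6 or more, e.g. 11 v 5 (30 points) | 0.105 |
| 8 or more, e.g. 12 v 4 (40 points) | 0.022 |

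Because the current protocol loosens the lower-band target, I varied K from 12 to 24. The probability of 4 or more stays at 0.30 to 0.34, and of 6 or more at 0.08 to 0.11.

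**Effect on the estimate.** Shift = band effect × (imbalance / 20), where the band effect is the difference between bands in percentage change in AUC, given baseline AUC. The documents give no value, so 5 to 15 points is an assumption. For a 4-subject imbalance:

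- 5 points: 5 × 4/20 = 1.0
- 10 points: 10 × 4/20 = 2.0
- 15 points: 15 × 4/20 = 3.0

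That is 0.16 to 0.47 standard errors (1.0/6.32 to 3.0/6.32), or 6% to 17% of the 18.1-point design difference.

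**Type I error.** I used 20,000 simulated trials per scenario, with K = 16, total SD 20, and band effects of 0, 5, 10 and 15. The rejection rate under the null was 0.099 to 0.103, with or without eGFR band in the model. Conditional on a realised imbalance it can differ: with a band effect of 10, the approximate rate is 0.107 for a 4-subject imbalance and 0.128 for a 6-subject one.

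**Power with eGFR in the model.** Let r be the partial correlation of eGFR with the outcome. The residual SD becomes 20 × √(1 − r²). The added covariate costs one degree of freedom (37 to 36) and inflates the variance of the treatment contrast by about 1 + 1/38 = 1.026. Noncentrality = 18.1 / [20 × √(1 − r²) × √(0.1 × 1.026)].

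| r | Noncentrality | Power |
|---|---|---|
| eGFR not in model | 2.86 | 87.8% |
| 0 | 2.82 | 87.0% |
| 0.16 | 2.86 | 87.8% (break-even) |
| 0.2 | 2.88 | 88.2% |
| 0.3 | 2.96 | 89.6% |
| 0.4 | 3.08 | 91.6% |

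Leaving out the degree of freedom and the inflation would give 88.9%, 90.3% and 92.2% at 0.2, 0.3 and 0.4, which is too favourable.

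**Linking the two scales.** With 40% in the lower band, r = band effect × √(0.4 × 0.6) / 20. Band effects of 5, 10 and 15 give r of about 0.12, 0.24 and 0.37. Break-even at r = 0.16 is a band effect of 0.16 × 20 / 0.490 = 6.5 points. The simulation agrees. Power without and with eGFR band was 0.867 and 0.859 (no effect), 0.873 and 0.868 (5 points), 0.865 and 0.874 (10 points), and 0.867 and 0.900 (15 points).

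**The case against.** The strongest reply is that nothing is wrong with the primary test. Randomisation protects its level, its standard error already allows for chance imbalance, and the illustrated shift is under half a standard error. That stands.

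It is also fair that prognostic value is assumed. Protocol 3.2.2 justifies the quotas by representation of both ends of moderate renal impairment, which makes no claim that eGFR predicts glucose response. One might point to the metformin adjustments tied to eGFR in Protocol 3.1.4. However, those for screening eGFR of 30 to 44 are made at Visit 2 (Day -14), before the baseline MMTT on Day -5, so baseline AUC should capture at least part of their effect. Later drift, or changes after a decline on study, would not be captured, but the documents do not quantify either.

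The omission of eGFR from stratification is deliberate and disclosed, and insulin stratum, which is stratified on, is also missing from the primary model. SAP 3.4.3 is redacted, so one cannot say that no supportive analysis uses eGFR. These points limit the weight of the concern. They do not give a reason against adjusting for a baseline variable that is already measured.

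A reader might infer that a material imbalance is likely. Only a 2-subject difference is; 4 or more has about a one-in-three chance and 6 or more about one in ten. A reader might also infer that adjustment is free or can only help. It lowers power slightly when eGFR is weakly prognostic, including at the low end of the range assumed here.

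**Conclusion.** The point holds as a cheap improvement, not as an error in the plan. Quotas without stratification or adjustment leave the primary contrast exposed to a chance eGFR imbalance, with the consequence confined to precision and conditional balance. The documents do not support reading it as a biased or invalid primary analysis.

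The trade-off is a loss of about 0.8 points of power if eGFR is not prognostic, against gains of about 0.4 to 3.8 points at partial correlations of 0.2 to 0.4, plus protection against a realised imbalance. This rests on the planned SD of 20, 20 completers per arm, and an assumed prognostic strength on which the documents are silent.

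**What to change.** In SAP 3.4.1.3, add screening eGFR as a continuous covariate beside baseline AUC, fixed before unblinding, and align Protocol 4.8.3.1. Leave the randomisation unchanged. The lesser alternative is to keep the two-term primary model and pre-specify the eGFR-adjusted model as a sensitivity analysis.

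The cost is one model term, one degree of freedom and a slight variance inflation, with no new data. The SAP needs revising in any case: it is written to Amendment 2 and still describes an interim analysis that the current protocol does not plan.

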2.3 Treatment Assignment and Blinding

An IWRS will be used for randomization to a treatment group and assignment of blinded investigational product kit numbers. Forty (40) subjects will be randomized using a 1:1 ratio to receive either MEDI0382 or placebo with the randomization stratified [REDACTED]

This is a double-blind study in which MEDI0382 and placebo prefilled syringes are identical except the fill volumes are not identical/indistinguishable in appearance. The different fill volumes of MEDI0382 and placebo prefilled syringes and the relative position of the plunger rods will be visually distinct during administration. Although not perfect, the blind will be maintained by having the study drug administered at the clinical site by an unblinded person not involved in the treatment or clinical evaluation of the subjects. This unblinded person will also dispense and receive drug from the subject and reconcile drug accountability. An unblinded site monitor will interact with site unblinded personnel to maintain study blind.

2.4 Sample Size

Forty subjects (20 completers in the MEDI0382 group and 20 completers in placebo group) will provide > 85% power to detect 18.1% difference between the two treatment groups in percentage change in the MMTT glucose AUC from baseline (Day -5) to the end of 32 days of treatment (Day 32), with a two-sided significance level of 0.1 and assuming the standard deviation of 20%.

3 STATISTICAL METHODS

3.1 General Considerations

Data will be presented in data listings sorted by insulin strata, treatment, subject number and date collected, where appropriate. Tabular summaries will be presented for each treatment and for insulin strata within treatment. Categorical data will be summarized by treatment and for insulin strata within each treatment with the number and percentage of subjects within each category. In general, continuous variables will be summarized by treatment and insulin strata within treatment with descriptive statistics including mean, standard deviation, median, minimum, and maximum. Safety variables will generally be summarized by treatment across insulin strata.

All available data will be included in the analyses and missing data will not be imputed except as specified in the calculation of the AUC values. Unless specified otherwise, baseline values will be defined as the last valid assessment prior to the first administration of study medication.

All statistical tests will be 2-sided at an alpha = 0.10 significance level unless stated otherwise. There will be no adjustment for multiplicity.

Data analyses will be performed using SAS[®] version 9.3 or higher (SAS Institute Inc., Cary, NC) in a UNIX environment. The analytical results generated from SAS programs will follow MedImmune SAS programming standards and will be validated according to MedImmune SAS validation procedures.

3.2 Analysis Populations

The analysis populations are defined in Table 3.2-1.

Table 3.2-1 Analysis Populations

Population	Description
Intent-to-treat (ITT) population	Subjects who receive any study investigational product will be included in the ITT population and subjects will be analyzed according to their randomized treatment group.

Table 3.2-1 Analysis Populations

Population	Description
As-treated population	Subjects who receive any study investigational product will be included in the as-treated population and subjects will be analyzed according to the treatment they actually receive.
Pharmacokinetic (PK) population	The PK population includes all subjects who received at least 1 dose of investigational product and had at least one PK sample taken with a value above the lower limit of quantitation.

3.3 Study Subjects

3.3.1 Subject Disposition and Completion Status

A summary of subject eligibility and randomization (including summary of subjects randomized but not treated) as well as treatment administered and insulin strata will be provided. In addition, disposition of subjects throughout the study with respect to completion of treatment and follow-up will be provided.

3.3.2 Demographics and Baseline Characteristics

Demographic information related to sex, age, race, weight, height, and body mass index (BMI) will be presented by insulin strata and treatment group and for all subjects combined. A summary of baseline disease characteristics may include, but not be limited to screening eGFR, number (%) with $30 \leq eGFR < 45$ ml/min/1.73 m² and number (%) with $45 \leq eGFR < 60$ ml/min/1.73 m², HbA1c, and insulin dose (insulin strata), and oral anti-hyperglycemic medications.

3.3.3 Study Drug Exposure

The number of doses and total dose received will be summarized by insulin strata for each investigational product (MEDI0382 or Placebo) by descriptive statistics and frequencies.

3.3.4 Concomitant Medications

Concomitant medications will be coded using the current WHO Drug Dictionary enhanced (WHO-DD). The number and percentage of subjects who took concomitant medications for the highest anatomical therapeutic chemical (ATC) class and preferred term will be summarized by study part and treatment for the As-treated Population. The summary of concomitant medications will include all concomitant medications taken on or after the date of first dose of investigational product or any concomitant medication started prior to first dose of investigational product that continued beyond the date of first dose of investigational product.

3.4 Efficacy Analyses

3.4.1 Primary Efficacy Endpoint(s) and Analyses

3.4.1.1 Primary Efficacy Endpoint(s)

Percentage change in glucose area under the curve (AUC) as measured by a standardized mixed-meal tolerance test (MMTT) from baseline (Day -5) to the end of 32 days of treatment.

3.4.1.2 Handling of Dropouts and Missing Data

Subjects who do not have a valid baseline evaluation or a valid Day 32 MMTT evaluation will not be included in the analysis.

3.4.1.3 Primary Efficacy Analysis

The primary efficacy analysis will be performed using the ITT population. The primary efficacy endpoint, percentage change in MMTT glucose AUC from baseline (Day -5) to the end of treatment evaluation (Day 32) will be analyzed using an analysis of covariance (ANCOVA) model. The model will include fixed effect for treatment (MEDI0382 or Placebo) with the baseline AUC used as a covariate. The treatment groups will be considered statistically significant if the two-sided significance level is less than 0.10.

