4.8.3 Efficacy

4.8.3.1 Primary Efficacy Analysis

The primary efficacy analysis will be performed using the ITT population. The primary efficacy endpoint, percentage change in MMTT glucose AUC from baseline (Day -5) to the end of 32 days of treatment will be analysed using an analysis of covariance (ANCOVA) model. The model will include fixed effect of treatment and baseline AUC as a covariate. The difference of the percent change in glucose AUC between the two treatment arms will be compared with a two-sided significance level of 0.10.

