3.4.1.4 Subgroup Analyses

Two subgroup analyses will be performed if there are at least 6 subjects in the smallest subgroup. The analysis will be an analysis of covariance with fixed effects for treatment (MEDI0382 or Placebo), subgroup, and treatment by subgroup interaction with the baseline AUC used as a covariate. The subgroups that will be included in the analysis are:

- Insulin strata (insulin dose ≥ 20 U/day and insulin dose < 20 U/day)
- Baseline HbA1c category ($< 8\%$ and $\geq 8\%$)

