3.4.2.3 Secondary Efficacy Analyses

The secondary efficacy endpoints will be analyzed with ANCOVA, similar to that used for the primary endpoint.

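### Randomisation is stratified by insulin dose but the primary ANCOVA omits the stratum, so if the stratum predicts outcome the test is conservative and a little power is forgone

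*SAP*

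**What the plan says.** SAP 2.2 describes the allocation: "Forty (40) subjects across multiple study sites will be randomized in two strata (Insulin dose ≥ 20 U/day or Insulin dose < 20 U/day". SAP 2.3 confirms 1:1 stratified randomisation: "Forty (40) subjects will be randomized using a 1:1 ratio to receive either MEDI0382 or placebo with the randomization stratified". The text that follows in 2.3 is redacted, so the factor itself is visible only in 2.2.

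The primary model has two terms. SAP 3.4.1.3: "The model will include fixed effect for treatment (MEDI0382 or Placebo) with the baseline AUC used as a covariate". Protocol 4.8.3.1, repeated in the synopsis: "The model will include fixed effect of treatment and baseline AUC as a covariate". None of these model sentences is redacted.

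The SAP uses the stratum elsewhere. Section 3.1: "Tabular summaries will be presented for each treatment and for insulin strata within treatment". Section 3.4.1.4 fits the stratum to the primary endpoint, but only as a subgroup analysis: "The analysis will be an analysis of covariance with fixed effects for treatment (MEDI0382 or Placebo), subgroup, and treatment by subgroup interaction". That model is run only if the smallest subgroup has at least 6 subjects.

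The primary model also carries over to other endpoints. SAP 3.4.2.3: "The secondary efficacy endpoints will be analyzed with ANCOVA, similar to that used for the primary endpoint".

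**The concern.** Randomising 1:1 within strata forces the arms to be close to balanced on insulin dose. The treatment estimate therefore varies less over repeated trials than it would under simple randomisation. An ANCOVA without the stratum does not know this. It counts the between-stratum variation as residual error and reports a standard error larger than the true one.

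This matters only to the extent that the stratum predicts the outcome beyond baseline AUC, which is already in the model. If it does, the confidence interval is wider than the design warrants, the test at a nominal 0.10 rejects less often than that under the null, and a real effect is somewhat more likely to be missed in a 40-subject trial. Type I error is not inflated and the estimate is not biased.

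**Working it through.** **Inputs from the documents.** 20 completers per arm, difference 18.1 percentage points, SD 20, two-sided alpha 0.10, stated power > 85% (SAP 2.4, Protocol 4.8.2). Two strata with 1:1 allocation (SAP 2.2, 2.3). At least 20 of 40 subjects on ≥ 20 units/day (Protocol 4.1.2).

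**Assumed, because the documents do not give them.** R², the share of residual variance explained by the stratum beyond baseline AUC; the block size; the exact stratum split; the number of subjects lost.

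**1. The plan's own power.** SE = 20 × √(2/20) = 6.32. The normal approximation gives 88.8%. The noncentral t gives 87.8%, with 38 df or with the ANCOVA's 37 df. The stated > 85% is reproduced.

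**2. Formula for the omitted stratum.** With exact balance in each stratum, the true variance of the estimate is (1 − R²) times the variance the model reports. Hence, approximately:

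type I error = 2 × [1 − Φ(1.645 / √(1 − R²))]

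- R² = 0.05: 1.645 / √0.95 = 1.688, giving 0.091
- R² = 0.10: 1.645 / √0.90 = 1.734, giving 0.083
- R² = 0.20: 1.645 / √0.80 = 1.839, giving 0.066
- R² = 0.30: 1.645 / √0.70 = 1.966, giving 0.049

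**3. Simulation.** 40,000 trials per setting, total residual SD held at 20, Monte Carlo SE of a power figure about 0.2 point. The planned ANCOVA is compared with the same model plus the stratum.

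Setting A: strata of 20 and 20, exact 1:1 in each, no loss.

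| R² | Type I error, stratum omitted | Power, omitted | Power, included | Gain (points) |
|---|---|---|---|---|
| 0 | about 0.10 | 86.9% | 86.8% | −0.1 |
| 0.05 | 0.090 | 87.6% | 88.4% | 0.8 |
| 0.10 | 0.081 | 88.0% | 89.9% | 1.9 |
| 0.20 | 0.065 | 89.5% | 92.8% | 3.3 |
| 0.30 | 0.050 | 90.7% | 95.3% | 4.6 |

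At R² = 0.20 the mean reported SE is 6.40 and the true SE is 5.72. The formula in step 2 gives 6.32 and 6.32 × √0.80 = 5.66.

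Setting B: strata of 24 and 16, blocks of 4, four subjects lost at random, 36 analysed.

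| R² | Type I error, stratum omitted | Power, omitted | Power, included | Gain (points) |
|---|---|---|---|---|
| 0 | about 0.10 | 83.6% | 83.3% | −0.3 |
| 0.10 | 0.084 | 84.5% | 86.7% | 2.2 |
| 0.20 | 0.068 | 85.4% | 89.8% | 4.4 |
| 0.30 | 0.056 | 86.7% | 92.9% | 6.2 |

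A separate run of 20,000 trials gave a gain of 0.8 point at R² = 0.05 in setting B. The lower power level in B comes from the lost subjects, not from the model. Strata of 28 and 12 gave gains within 0.2 point of these.

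**4. Is stratification the cause?** In a separate run at R² = 0.20 with 10,000 trials, type I error without the stratum term was 6.1% under stratified allocation and 9.5% under unstratified allocation. With the term included, stratified allocation gave 9.5%. The conservatism therefore comes from stratifying without adjusting. It persisted with strata of 26 and 14 (6.6% omitted, 9.9% included) and with baseline AUC correlated 0.4 with the stratum (8.1% and 10.4%).

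**5. What each R² means.** With equal strata, the gap between stratum means in percentage change is 2 × 20 × √R²:

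- R² = 0.05: 8.9 points
- R² = 0.10: 12.6 points
- R² = 0.20: 17.9 points
- R² = 0.30: 21.9 points

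R² = 0.20 already implies a stratum gap about as large as the assumed treatment effect of 18.1, so the lower rows are the more plausible ones.

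**The case against.** The strongest objection is that this is a small, conditional efficiency point. No stated figure is wrong, the error is conservative, and nothing in the documents shows that insulin dose predicts percentage change once baseline AUC is in the model. Each subject is compared with their own baseline, and insulin users take their usual or current breakfast insulin with the test meal (Protocol 4.3.1.1). The upper rows of the tables need stratum gaps near or above the treatment effect. At R² = 0.02, a gap of 5.7 points, a run of both settings gave a gain of only 0.3 point. All of this stands, and it is why the headline size is 1 to 2 points and not 5 or 6.

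There is some reason to expect a relation. Insulin acts directly on the meal response, carbohydrate counters adjust their dose to the drink, and Protocol 3.1.4 requires insulin to be cut after certain hypoglycaemic events, which baseline AUC cannot reflect. That makes R² above zero plausible but does not supply a value.

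Two further points concern the text. Redaction follows the stratification sentences, and SAP 3.4.3 is wholly blacked out, so a rationale or a sensitivity analysis may exist out of sight. That is fair: one can say only that none is visible. The subgroup model in SAP 3.4.1.4 does include the stratum, but it adds an interaction, depends on subgroup size and is not the primary test, so it does not repair the primary analysis.

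Finally, no size has been computed for the secondary endpoints. The case for adding the term there is consistency with the design.

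**Conclusion.** The point holds. The trial randomises within insulin strata, and the primary model leaves the stratum out without a visible reason. To the extent the stratum is prognostic beyond baseline AUC, the reported standard error is too large and the test is conservative. The size cannot be fixed from the documents. It is about 1 to 2 points of power, with true type I error of 0.08 to 0.09, at the more plausible R² of 0.05 to 0.10. At R² of 0.20 to 0.30 it rises to 3.3 to 4.6 points with no loss, or 4.4 to 6.2 points with four subjects lost. If R² is zero, including the term costs at most 0.3 point.

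Confidence is high on the omission and the direction of the error. The size rests on the assumed R², stratum split, block size and losses. A significant result from the plan as written would remain valid. The change is an inexpensive improvement worth making, not the repair of an invalid analysis.

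**What to change.** In SAP 3.4.1.3, Protocol 4.8.3.1 and the synopsis, state the model as:

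> Fixed effects for treatment (MEDI0382 or placebo) and for insulin stratum as randomised (≥ 20 U/day, < 20 U/day), with baseline AUC as a covariate.

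Use the same stratum term in the ANCOVAs for HbA1c, fasting glucose and body weight. It does not apply to time in range where the protocol's Wilcoxon rank-sum test is used. If the sponsor prefers to leave the stratum out, the SAP should say why. Either way, settle it before unblinding.

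The analysis cost is one degree of freedom and no new data. The SAP must be revised in any case, because its section 4 still plans an interim analysis that Protocol 4.8.7 no longer includes. On the protocol side, if the change is judged substantial, Protocol 7.4 requires an amendment with ethics approval and, where local rules ask for it, regulatory approval. The wording change could go into the next amendment.
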